## 2 Study Objectives

### *Primary objective:*

To assess the acceptability of a novel, minimally invasive esophageal mucosal sampling technique, the Cytosponge, in subjects undergoing surveillance after radiofrequency ablation. Based on previous data, we hypothesize that the sponge-based sampling technique will be associated with low levels of patient distress, and will be preferred by patients, when compared to standard sedated upper endoscopy, for surveillance of their esophageal mucosa.

### *Secondary objective:*

To assess the operating characteristics of this technique against a gold standard of upper endoscopy with biopsies for endoscopic surveillance in subjects with a history of successful radiofrequency ablation for dysplastic BE. We hypothesize that the assay will demonstrate both a sensitivity and specificity of >90% in the detection of recurrent BE following radiofrequency ablation. Further, we expect higher accuracy in those with a larger burden of recurrent disease.

## 3 Study Design

### 3.1 General Design

This is cross-sectional study of subjects with dysplastic BE who have undergone successful endoscopic ablation with RFA, to assess the utility of the Cytosponge assay as a non-endoscopic method for monitoring the post-ablation patient. In addition, we will enroll a small cohort of up to 50 subjects with a current diagnosis of BE to collect pilot data for a larger scale study. Subjects presenting to UNC Hospitals for routine endoscopic examinations for current BE or after successful ablation will be offered enrollment in the study. After informed consent, and the same day as the endoscopic procedure, the subject will undergo administration of the Cytosponge assay. The patient will then undergo routine endoscopic surveillance, using a standard Seattle biopsy surveillance protocol. The Cytosponge will be placed in fixative and shipped to the [name] laboratory for processing according to their established protocols. Tissue biopsies will undergo standard processing and H&E staining, with assessment by expert gastrointestinal pathologists at UNC. The primary outcome variables will be sensitivity and specificity of the novel assay, compared against the gold standard of the presence of recurrent BE as detected by upper endoscopy with biopsies. Secondary outcomes include acceptability of the nonendoscopic assay to the patient (assessed by a standardized tool, the Impact of Events Scale, as well as a visual analogue scale), and likelihood of assay positivity as a function of amount of residual disease (as measured by Prague criteria).

[figure not shown]
If the initial administration of the Cytosponge demonstrates an inadequate sample, defined as a sample that does not demonstrate at least one columnar cell on hematoxylin & eosin staining, repeat Cytosponge administration will be performed at 30 days (+/- 10 days) from the initial administration.

Subject recruitment will be from consecutive eligible patients presenting for routine care surveillance endoscopy of current BE or following endoscopic ablation of BE. Potentially eligible subjects will be contacted by telephone in advance of their procedure and their interest in study participation assessed. Subjects interested in participating will be asked to present to the endoscopy unit one hour prior to their scheduled procedure. At that time, inclusion and exclusion criteria will be reviewed, and eligible subjects will give informed consent. Subjects will then undergo the Cytosponge assay. Following Cytosponge assay, subjects will complete the procedure acceptability measures described below. Subjects will then attend their usual surveillance endoscopy session. Upper endoscopy will be performed and biopsies taken as part of routine care. Importantly, no record of the results of the standard endoscopy and biopsies will be provided to those assessing the Cytosponge results and these individuals will be masked to all clinical data. Similarly, the pathologists interpreting the histological specimens from the endoscopy will have no knowledge of the outcomes of the Cytosponge assay. Only the study biostatistician will have access to these data.

Primary assessment of acceptability will be via the Impact of Events Scale. This widely used scale was developed to assess the distress associated with a specific life event. It includes measures of both the intrusiveness of the event, and any avoidance responses by the subject in response to the event. Final scores are between 0-75, with low scores demonstrating a low impact of the event. The scale will be administered 7 days after the sampling in order to allow the subjects to have time to reflect on the experience and to compare with the EGD. Secondary acceptability outcomes will include a visual analogue scale of acceptability of the Cytosponge, performed after the Cytosponge is administered. Also, the subject will be asked whether he/she would be willing to repeat the assay, and, assuming similar accuracy between Cytosponge and upper endoscopy, whether he/she would rather undergo surveillance by Cytosponge or standard EGD with biopsies.

There are no plans for repeat testing or duplicate enrollment. Enrolled subjects will be administered the cytosponge one time, on the date of an endoscopy scheduled for routine care, prior to the endoscopy. Subjects can only participate one time. The only exception is for subjects who have an inadequate sample on the initial Cytosponge. These subjects will be asked to return for repeat Cytosponge administration 30 days (+/- 10 days) after the initial administration.

### 3.2 Protocol Map

### **3.3 Primary Outcomes**

The primary outcome variables will be sensitivity and specificity of the novel assay, compared against the gold standard of the presence of recurrent BE as detected by upper endoscopy with biopsies.

### **3.4 Secondary Outcomes**

Secondary outcomes include acceptability of the non-endoscopic assay to the patient (assessed by a standardized tool, the Impact of Events Scale, as well as a visual analogue scale), and likelihood of assay positivity as a function of amount of residual disease (as measured by prague criteria).

## **4 Subject Selection and Withdrawal**

### **4.1 Inclusion Criteria**

1. Male or female subjects, age 18-80 years,
2. Meets the following:
  - 2.1. Previous diagnosis of BE with dysplastic LGD or HGD, as evidenced by both classical endoscopic appearance of salmon-colored mucosa in the tubular esophagus, as well as endoscopic biopsies from the involved areas demonstrating columnar metaplasia with goblet cells. The diagnosis of dysplasia must have been confirmed by a second expert pathologist. Previous EMR of focal nodular HGD or superficial intramucosal cancer (IMC) is allowable, as long as the EMR specimen shows complete resection of any IMC with clear margins, and biopsies following ablation confirm excision of the lesion, **AND**
    - 2.1.1. A history of complete eradication of both dysplasia and intestinal metaplasia by radiofrequency ablation. Complete eradication is defined as a normal endoscopic appearance of the tubular esophagus, and histologic confirmation by biopsies in 4 quadrants every cm from throughout the length of the previous BE (post-RFA cohort). **OR**
  - 2.2. Current diagnosis of BE, presenting for routine care endoscopy (BE cohort).
3. Good general health, with no severely debilitating diseases, active malignancy, or condition that would interfere with study participation.

Exclusion Criteria:

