- Have a history of esophageal stricture,
- Have any history of esophageal varices, liver impairment of moderate or worse severity (Child's-Pugh class B & C), or evidence of varices noted on any past endoscopy,
- Have any history of esophageal surgery (except uncomplicated fundoplication), and history of coagulopathy, with INR >1.3 and/or platelet count of <75,000.

Importantly, all patients enrolled in this study will have previously and recently received an upper endoscopy during which absence of findings putting the subject at higher risk for these theoretical concerns (conditions such as varices and stricture) will be documented.

Cytosponge administration will occur after an overnight fast to minimize the possibility of aspiration of any gastric contents. Every administered sponge will be assessed post-procedure for signs of fracture or incomplete retrieval of the sponge. In the unlikely case of incomplete retrieval, the sponge will be retrieved with a Roth net at the standard of care endoscopy which will routinely immediately follow the administration of the sponge per the study protocol. Any bleeding noted, either clinically following the sponge administration or due to blood on the sponge itself, will be similarly investigated, and, as necessary, treated during the subsequent endoscopy. Because study inclusion/exclusion criteria are designed to exclude those at highest risk for a bleeding complication, the risk of bleeding in this study should be extremely low.

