### **4.2 Exclusion Criteria**

1. Current use of blood thinners such as coumadin, warfarin, clopidogrel, heparin and/or low molecular weight heparin (requires discontinuation of medication 7 days prior to and 7 days after esophagogastroduodenoscopy [EGD] and Cytosponge administration, aspirin use is OK).
2. Known bleeding disorder
3. For the post-RFA cohort, prior ablative therapy of the esophagus other than radiofrequency ablation (RFA), including photodynamic therapy (PDT), more than one session of spray cryotherapy, and any other ablation therapies is exclusionary. However, prior endoscopic mucosal resection (EMR) is acceptable and up to two prior treatments of thermal/coagulation therapy (other than RFA) for focal residual disease following otherwise successful RFA therapy is acceptable. The BE cohort must be treatment naive and have no history of ablation, but prior EMR is acceptable.
4. History of esophageal stricture precluding passage of the endoscope or sponge,
5. Pregnancy, or planned pregnancy during the course of the study,
6. Any history of esophageal varices, liver impairment of moderate or worse severity (Child's- Pugh class B & C) or evidence of varices noted on any past endoscopy,
7. Any history of esophageal surgery, except for uncomplicated fundoplication, and,
8. History of coagulopathy, with INR>1.3 and/or platelet count of <75,000.
9. Planned ablation therapy within 3 days of Cytosponge administration (endoscopic mucosal resection and submucosal dissection is OK).

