#### 5.1.1 Assessments

The following will be completed during the screening/enrollment visit:

- Eligibility review
- Informed consent
- Cytosponge administration
- Visual Analogue Scale
- Routine care upper endoscopy with biopsy
- Adverse event assessment
- Enrollment Case Report Form (eCRF): This captures demographics including race, ethnicity, gender, and year of birth, relevant BE medical history including documentation of endoscopic procedures received to date as well as pathology findings and endoscopic

history related to current diagnosis. This will also capture the date the Cytosponge was sent to the [name] Lab for analysis

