## 6.2 Statistical Methods

For the primary objective, to assess the acceptability of the novel mucosal sampling technique in subjects after successful ablation, we will assess the distribution of Impact of Events Scale scores, and the intrusiveness and avoidance subscales. We will generate measures of central tendency and distribution of these data. Bivariate analysis will be performed to assess for predictors of low tolerance of Cytosponge surveillance, and a logistic regression model created to assess these factors while controlling for potential confounders. Data will be compared to population norms using parametric statistics. VAS scores will be calculated, and measures of central tendency and distribution reported.

Subjects' preferences for Cytosponge vs. endoscopic surveillance, as well as willingness to undergo the procedure again, will be measured as proportions, with bivariate and multivariate analyses for predictors of preference performed.

For the secondary objective, to assess the operating characteristics of Cytosponge against a gold standard of upper endoscopy, initially 2x2 tables will be constructed demonstrating Cytosponge and the gold standard findings (Y/N for BE). Sensitivity, specificity, positive predictive value, negative predictive value and accuracy will be calculated. Because Cytosponge positivity may vary based on the burden of BE, we will perform sensitivity analyses, defining "positive" cases as those with recurrent BE of  $\geq 1$  cm in length, and then  $\geq 2$  cm in length, to assess impact of disease burden on operating characteristics. Multivariate models controlling for age, sex, period of time from last ablation, burden of residual disease, and other potential confounders will be constructed, to assess the impact of these factors on test accuracy. Although we do not expect to see an association between the degree of dysplasia and Cytosponge positivity, exploratory analyses will be performed using degree of dysplasia as a predictor variable, and Cytosponge positivity as the outcome variable.

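### The post-RFA cohort may include recurrences already known at enrolment, and the plan does not separate them, so the pooled PPV and NPV may not describe surveillance of patients in remission

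*Combined protocol and SAP*

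**What the plan says.** Section 4.1, item 2.1.1, admits a subject to the post-RFA cohort on the basis of "A history of complete eradication of both dysplasia and intestinal metaplasia by radiofrequency ablation". Eradication is defined carefully, by endoscopic appearance and biopsies, but it carries no date and is not tied to the last examination before enrolment.

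Other provisions bear on whether a recurrence found before enrolment can enter:

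- Section 3.1: "Subject recruitment will be from consecutive eligible patients presenting for routine care surveillance endoscopy of current BE or following endoscopic ablation of BE".
- Section 4.2, exclusion 3: "The BE cohort must be treatment naive and have no history of ablation, but prior EMR is acceptable". A previously ablated patient whose BE has returned can therefore enter only through the post-RFA cohort.
- Section 4.2, exclusion 9, lists "Planned ablation therapy within 3 days of Cytosponge administration (endoscopic mucosal resection and submucosal dissection is OK"). It names no cohort.
- Section 1.3.1 says that "all patients enrolled in this study will have previously and recently received an upper endoscopy". The purpose given is to document the absence of risk conditions such as varices and stricture, not the absence of BE.

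In the analysis, section 3.3 has the assay "compared against the gold standard of the presence of recurrent BE as detected by upper endoscopy with biopsies". Section 6.2 adds: "Sensitivity, specificity, positive predictive value, negative predictive value and accuracy will be calculated". Section 6.3 analyses everyone with a completed sponge and pathology from the study endoscopy. None of these distinguishes a known from a new recurrence. The enrolment form in section 5.1.1 does capture "documentation of endoscopic procedures received to date as well as pathology findings".

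**The concern.** The stated use (sections 1.1 and 2) is surveillance after successful RFA. The person facing that decision was clear at the last examination, and the question is whether BE has come back since. A subject whose recurrence was found at an earlier endoscopy is in a different position but counts here as an ordinary reference-positive case.

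PPV and NPV depend on the share of cases in the cohort. Adding known cases raises that share, so both measures move away from their values in remission. NPV matters most, because omitting an endoscopy after a negative sponge would rest on it. Sensitivity could shift too, if known recurrences are more extensive than new ones. Section 2 expects higher accuracy with larger burden.

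**Working it through.** **Inputs from section 6.1.** Sensitivity 87%; 81 recurrences; 25% recurrence; 324 post-ablation subjects; prior specificity 92-94%, midpoint 93% used here. **Not in the documents:** the share *k* of recurrences already known at enrolment. It is varied from 0 to 50%. The 25% is taken as the prevalence in the pooled cohort.

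**The plan's own figure.** 81 / 0.25 = 324, which reproduces.

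**Expected pooled counts.** There are 81 cases and 324 − 81 = 243 non-cases.

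- TP = 0.87 × 81 = 70.47; FN = 10.53
- TN = 0.93 × 243 = 225.99; FP = 17.01
- PPV = 70.47 / 87.48 = 80.6%; NPV = 225.99 / 236.52 = 95.5%

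**Remove the known recurrences, with sensitivity equal at 87%.** A known recurrence confirmed at the study endoscopy is reference-positive, so TN and FP do not change. Only TP and FN shrink, each by the factor (1 − k):

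- PPV = 70.47(1 − k) / [70.47(1 − k) + 17.01]
- NPV = 225.99 / [225.99 + 10.53(1 − k)]
- New cases = 81(1 − k); prevalence = new cases / (new cases + 243)
- Wald half-width for sensitivity = 1.96 × √(0.87 × 0.13 / new cases)

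| Known share k | New cases | Prevalence | PPV | NPV | Half-width (points) |
|---|---|---|---|---|---|
| 0 (same as pooled) | 81 | 25.0% | 80.6% | 95.5% | 7.3 |
| 20% | 64.8 | 21.1% | 76.8% | 96.4% | 8.2 |
| 25% | 60.75 | 20.0% | 75.7% | 96.6% | 8.5 |
| 50% | 40.5 | 14.3% | 67.4% | 97.7% | 10.4 |

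**Direction.** Pooling adds to TP and FN and leaves FP and TN alone. PPV therefore cannot fall and NPV cannot rise through pooling, whatever the two sensitivities are. Specificity, TN / 243, is untouched.

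**Sensitivity.** Pooled sensitivity = k × Se(known) + (1 − k) × Se(new). If the two are equal there is no shift. At k = 25%, with illustrative values:

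- Se(new) 84%, Se(known) 90%: 0.25 × 90 + 0.75 × 84 = 85.5%, which is 1.5 points above the value for new recurrences.
- Se(new) 70%, Se(known) 90%: 0.25 × 90 + 0.75 × 70 = 75.0%, which is 5 points above.

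A difference in sensitivity also partly offsets the NPV error. In the 84%/90% case, pooled FN = 60.75 × 0.16 + 20.25 × 0.10 = 11.745, so pooled NPV = 225.99 / 237.735 = 95.1%. For new cases only, NPV = 225.99 / (225.99 + 9.72) = 95.9%. The gap is 0.8 points, against 1.1 at equal sensitivity.

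**The case against.** The best defence is the recruitment frame. Subjects are consecutive attenders at routine surveillance endoscopy, and a patient with a recurrence already found and awaiting treatment is not the typical attender. The number may be small or zero. This stands: the documents show that such enrolment is permitted, not that it occurs.

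A reader might infer from exclusion 9 that the plan expects post-RFA subjects with known disease. The text does not support that. The item names no cohort, and the BE cohort, which has current disease and may be scheduled for treatment, explains it fully.

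It is also tempting to quote much lower PPVs by taking recurrence in remission as 15% or 10%. Starting from 25%, those rates leave 243 × 0.15 / 0.85 = 42.9 and 243 × 0.10 / 0.90 = 27 new cases. The known shares would then be about 47% and 67% of the 81. The 10% rate also lies below the 13-38% range in section 6.1.

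The burden route to inflated sensitivity is partly covered. Section 6.2 plans re-analysis at ≥1 cm and ≥2 cm, and models with burden and time from last ablation. These would expose sensitivity that depends on burden. They do not identify the patients in remission or give a PPV and NPV for them. Masking of readers, in section 3.1, does not alter case mix either.

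**Conclusion.** The gap is real and its effect is conditional. Nothing in sections 1.3.1, 3.1, 4.1, 4.2, 6.2 or 6.3 requires the last endoscopy before enrolment to be BE-free or separates known from new recurrences. If known recurrences enrol, PPV is overstated by about 4 points at a 20% known share and 13 points at 50%. NPV is understated by about 1 to 2 points over the same range, or less if known recurrences are also easier to detect. These sizes rest on sensitivity 87%, specificity 93%, 25% pooled recurrence and assumed shares. The direction rests only on known recurrences being confirmed as positive at the study endoscopy.

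A reader might go further and conclude that the planned sensitivity is biased. That needs known recurrences to be easier to detect, and the documents give no burden data for them. Specificity is not affected. Nor does this evidence justify replacing the all-subject analysis of sensitivity and specificity, which could lose a large part of the 81 planned cases. A pre-specified split is enough.

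**What to change.** Leave eligibility and the all-subject sensitivity and specificity analysis as they are. In section 6.2:

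1. Define, from the enrolment form history, a variable for the post-RFA cohort: BE-free at the last endoscopy before enrolment, or recurrence already known. Count a recurrence that was re-treated and cleared at the last endoscopy as BE-free.
2. Pre-specify sensitivity, specificity, PPV and NPV in the BE-free group, and take the surveillance PPV and NPV from that group.
3. Report sensitivity in the known-recurrence group separately, with the number of subjects in it.

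The cost is one derived variable and a short addition to the statistical text. The form itself is not in the documents, so confirm that it records BE status at the last endoscopy. The statistical price is precision: at a 25% known share the BE-free group holds about 61 cases, with a Wald half-width of 8.5 points against 7.3 at 81. If no known recurrences enrolled, the results do not change.

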### **4.2 Exclusion Criteria**

1. Current use of blood thinners such as coumadin, warfarin, clopidogrel, heparin and/or low molecular weight heparin (requires discontinuation of medication 7 days prior to and 7 days after esophagogastroduodenoscopy [EGD] and Cytosponge administration, aspirin use is OK).
2. Known bleeding disorder
3. For the post-RFA cohort, prior ablative therapy of the esophagus other than radiofrequency ablation (RFA), including photodynamic therapy (PDT), more than one session of spray cryotherapy, and any other ablation therapies is exclusionary. However, prior endoscopic mucosal resection (EMR) is acceptable and up to two prior treatments of thermal/coagulation therapy (other than RFA) for focal residual disease following otherwise successful RFA therapy is acceptable. The BE cohort must be treatment naive and have no history of ablation, but prior EMR is acceptable.
4. History of esophageal stricture precluding passage of the endoscope or sponge,
5. Pregnancy, or planned pregnancy during the course of the study,
6. Any history of esophageal varices, liver impairment of moderate or worse severity (Child's- Pugh class B & C) or evidence of varices noted on any past endoscopy,
7. Any history of esophageal surgery, except for uncomplicated fundoplication, and,
8. History of coagulopathy, with INR>1.3 and/or platelet count of <75,000.
9. Planned ablation therapy within 3 days of Cytosponge administration (endoscopic mucosal resection and submucosal dissection is OK).

### **4.3 Subject Recruitment and Screening**

Potential subjects will be identified during their GI clinic or procedure visits at their treating institutions. All subjects will be screened and enrolled using EC/IRB-approved and HIPAA compliant methods.

An investigator, study coordinator, or other qualified personnel will obtain written informed consent prior to any study procedures. Potential subjects will have an opportunity to carefully review the consent form. The details of the study will be reviewed verbally, and all questions will be answered to the satisfaction of the patient. Only adults with the ability to consent will be eligible for enrollment in this study. After the subject signs the consent, a copy of the signed consent will be provided to the subject. Once written consent has been obtained, the coordinator will collect demographic and historical information from the patient pertaining to history of Barrett's Esophagus and ablation therapy.

The consent process will be documented by the coordinator in the patient's study file.

